3.4.3 Surgical Prophylaxis

Secondary objective: To assess the efficacy of *Human-cl rhFVIII* in surgical prophylaxis

Secondary endpoints:

- Efficacy assessment of surgical prophylaxis intra-operatively (at the end of the surgery [= after last suture]) by the surgeon:

- Excellent: Intra-operative blood loss was lower than or equal to the average expected blood loss compared with the same type of procedure performed in a patient with normal haemostasis and of the same sex, age, and stature.
- Good: Intra-operative blood loss was higher than average expected blood loss but lower or equal to the maximal expected blood loss compared with the same type of procedure in a patient with normal haemostasis.
- Moderate: Intra-operative blood loss was higher than maximal expected blood loss compared with the same type of procedure performed in a patient with normal haemostasis, but haemostasis was controlled.
- None: Haemostasis was uncontrolled necessitating a change in clotting factor replacement regimen.

- Overall efficacy assessment of surgical prophylaxis taking both the intra- and post-operative assessment into account will be done by the surgeon and the haematologist at the conclusion of the post-operative phase*:

- *Excellent:* No post-operative bleeding or oozing that was not due to complications of surgery. All post-operative bleeding (due to complications of surgery) was controlled with *Human-cl rhFVIII*, as anticipated for the type of procedure.
- *Good:* No post-operative bleeding or oozing that was not due to complications of surgery. Control of post-operative bleeding due to complications of surgery required increased dosing with *Human-cl rhFVIII* or additional infusions, not originally anticipated for the type of

procedure.

- *Moderate*: Some post-operative bleeding and oozing that was not due to complications of surgery; control of post-operative bleeding required increased dosing with *Human-cl rhFVIII* or additional infusions, not originally anticipated for the type of procedure.
- *None*: Extensive uncontrolled post-operative bleeding and oozing. Control of post-operative bleeding required use of an alternate FVIII concentrate.

* For a definition see below.

For treatments and evaluations related to surgeries three phases will be considered:

- Pre-operative: any dose administered or sample drawn until 3 hours before start of surgery
- Intra-operative: any dose administered or sample drawn during surgery
- Post-operative: any dose administered or sample drawn after the end of the surgery (end of surgery is defined as “last suture”) until ≥ 2 (minor surgeries) or ≥ 6 days post-surgery (major surgeries), until healing is complete and the subject returned to his regular treatment.

For all surgical procedures performed during the trial, the following data will be collected:

- Location (site) and type (planned or emergency) of surgery
- Severity of surgery (minor or major)
- Expected duration of surgical procedure
- Actual BW prior surgery (kg)
- Actual duration of surgical procedure (start and end times, i.e. skin to skin)
- Pre-, intra-, and post-operative FVIII plasma levels: FVIII:C determined by central lab (CHR and OS assay) and local lab (local standard method) within 30 min before and after each administration (pre-, intra- and postoperative), where in case of intra-operative administration this is only mandatory for major surgeries and in case of post-operative doses this is only mandatory for the first 3 doses after a major surgery
- Average and maximal expected blood loss for the planned surgical procedure and for the same procedure in a subject with normal haemostasis and of the same sex, age, and stature
- Blood loss (mL) estimation: Average expected, maximal expected and actual
- Any wound haematomas and whether they require surgical evacuation
- Laboratory tests: haematology and clinical chemistry before and 24h after end of surgery
- Vital signs (pre-, intra- and postoperatively)
- Details on concomitantly administered products including any blood/blood product transfusions but excluding drugs given for routine anaesthesia
- Details of administered dose(s) of *Human-cl rhFVIII* given pre-, intra- and/or post-operatively, including dates, times, and batch number.
- Brief narratives describing the outcome and efficacy of the interventions

3.4.4 **Resource use**

Further objective: To examine the resource use of patients treated with *Human-cl rhFVIII*

The following parameters will be basis of a resource use analysis:

- Use of FVIII concentrates:
Prophylaxis or on-demand, dose per kg body weight, the frequency of injection, duration of treatment, any change in treatment regimen.
- Bleeding episodes: location, severity and duration.
- Inhibitor status, any change in FVIII use, use of other haemostatic agents, hospitalisation (including ward type) and its duration.
- ITI: ITI regimen details (regimen type, FVIII use, dose per kg body weight, the frequency of injection, duration, other haemostatic agents, patients' inhibitor levels).
- CVAD (Central Venous Access Device): CVAD type, hospitalization (including ward type) and duration, surgical procedures, complications due to CVAD use and management of the complication.
- Surgery prophylaxis: dosage and duration of treatment with FVIII for surgery prophylaxis including details on the type of surgery.

The aforementioned resource parameters are collected as part of primary and secondary end points within the study. The same data will also be used to analyse resource use

In addition non-medical resource use data regarding employment, household tasks and 'care' time for caregivers will be collected in the diary.

The analysis of non-medical resource use data and further analysis of medical resource use data beyond the planned clinical analysis is not the objective of this analysis plan.

3.4.5 Determination of FVIII:C Levels

Central lab data:

FVIII:C will always be determined by two independent and commonly used laboratory assay techniques:

- The chromogenic (CHR) assay and the
- One-stage (OS) assay

All recovery calculations will be based on data from either assay; the chromogenic assay is however regarded as the more advanced method yielding the more accurate results.

Routine lab data:

For ITI patients' routine lab data will be used to determine criteria for successful treatment (recovery, half-lives). These data will usually be generated from routine labs and diverse assays.

3.4.6 Actual and Labelled Potencies

For all batches of *Human-cl rhFVIII*, the actual potencies, i.e. the content of FVIII expressed as IU, are provided by the central laboratory; these data will be provided to the statistician in order to be available for the analysis. The actual potencies will be determined using both assay methods, CHR and OS, and used accordingly for calculations based on each assay. Should the central laboratory not provide one single potency determination per lot per assay, the potency for one lot with one assay will be calculated as the geometric mean of the values provided for the lot/ assay method.

Calculation of recovery for non-ITI patients will be based on the actual potency whereas dosing will be based on the labelled potency.

3.4.7 **Incremental Recovery**

Investigations of incremental recovery (optional) can be done with the first *Human-cl rhFVIII* administration (40 IU FVIII/kg BW, labelled potency), or within the first three months after treatment start with *Human-cl rhFVIII*, but in either case in a non-bleeding patient. They are recommended being controlled every 6 months thereafter. At these visits, blood samples for the calculation of the incremental recovery will be taken before study drug injection and 0.25, and 1 hours after end of injection.

3.4.8 **Other non-routine laboratory data**

The following non-routine laboratory data will be collected. However, the details on variables supplied by central laboratories are not yet known at the time point of creation of this version of the analysis plan:

- Immunogenotyping: F8 gene mutation analysis (mandatory), categorization in null/non-null and high/low risk mutation, HLA-typing, immune response gene profiling, F8 ethnic haplotype determination (optional), (EDTA blood)

The following data generated in the study will not be analysed under this SAP:

- RNA expression analysis (optional) (whole blood, RNase-free conditions)
- *In vitro* immunogenicity of FVIII products (optional) (citrate blood)

3.4.9 **Clinical Safety**

Clinical safety and tolerability will be assessed by monitoring vital signs, adverse events and laboratory parameters, including inhibitors against FVIII:

- Vital signs (blood pressure, heart rate, respiratory rate, body temperature) will be assessed at the following time-points:
 - at screening,
 - before and – in case IMP was injected – 30-60 minutes after the end of the infusion at the 3-monthly visits,
 - before and – in case IMP was injected – 30-60 minutes after the end of the infusion at the completion visit.
 - With respect to surgical procedures vital signs will be recorded before, during and on the first postoperative day.
- Physical examination
 - at screening,
 - once every 6 months and
 - at study completion.
- Adverse Events will be monitored throughout the whole study period and the following data will be collected:
 - Reported term
 - Associated MedDRA terms (Low Level Term, Preferred Term, System Organ Class)
 - Date of onset
 - Severity (mild, moderate or severe)
 - Seriousness (non-serious or serious)
 - Causality (probable, possible, unlikely, not related, unclassified)

- Outcome (recovered/resolved, recovering/resolving, not recovered/not resolved, recovered/resolved with sequelae, fatal, unknown)
 - Date of outcome
 - Actions taken in general (none, drug therapy (other than IMP) started, test performed, other (to be specified)) and on study drug (none, drug withdrawn, dose reduced, dose increased)
- The safety lab panel consists of the following measurements:
 - Haematology: red blood cell count (RBC), white blood cell count (WBC), haemoglobin (HB), hematocrit (HCT), and platelet count.
 - Clinical chemistry: alanine amino transferase (ALAT), aspartate transaminase (ASAT), serum creatinine (CREA).

The time-points for sampling for these lab parameters are:

	Screening	3-monthly visits (± 2 weeks)	Surgery (pre- and post surgery)
Haematology	✓	✓	✓
Chemistry	✓	✓	✓

4 STUDY DESIGN

4.1 General Design and Plan

This study is a prospective, open-label, multi-national, multi-center phase III study in previously untreated patients with severe Haemophilia A.

For each patient, the exposure to *Human-cl rhFVIII*, the efficacy of *Human-cl rhFVIII* in the prevention and the treatment of bleeds, the frequency of break-through bleeds in case of prophylactic treatment, the efficacy in surgical prophylaxis, and the overall safety and tolerability of *Human-cl rhFVIII* will be assessed. In the course of the follow-up visits (i.e. every 3-4 EDs until ED 20, then every 10-12 EDs until ED 100), scheduled to be performed after the Screening Visit, FVIII inhibitor levels will be assessed for each patient.

A patient completes the study by reaching 100 EDs, or after a maximum study participation period of 5 years from screening. In patients who develop FVIII inhibitors and start ITI (Immune tolerance induction; high doses of FVIII) treatment, the maximum length of ITI will be 36 months. In patients undergoing surgical interventions, treatment details will be documented for the pre-, intra-, and post-operative phase, respectively.

4.2 Sample Size

100 evaluable previously untreated patients (PUPs) will be enrolled in this study.

No inferential analysis involving formal testing is planned in this non-controlled study.

Consequently, no formal sample size estimation was performed, but the sample size was chosen to satisfy CHMP recommendations.

According to the CHMP “Guideline on the Clinical Investigation of Recombinant and Human Plasma-Derived Factor VIII Products” (EMA/CHMP/BPWP/144533/2009) [1], a minimum of 50 PUPs evaluated for efficacy and safety during at least 50 EDs, connected with a post-approval commitment to follow up at least 100 PUPs (50 from efficacy/safety trial and 50 new) for a minimum of 100 ED, is necessary.

4.3 Randomization and Blinding

Not applicable.

4.4 Study Assessments

For assessments directly related to the evaluation of the primary and secondary endpoints, please refer to section 3.4 (Assessment of Objectives).

The following parameters will be assessed to allow a meaningful characterisation of the study population and to collect background information required for medical evaluation of study events:

- Subject demographics and baseline characteristics:
including ethnicity, age, height, weight, family history of haemophilia and inhibitors against FVIII.
- F8 gene mutation analysis including null/non-null specification
- Immunogenotyping
(HLA-typing, immune response gene profiling, F8 ethnic haplotype determination)
- RNA expression analysis
- FVIII level and recovery determination
- Half-life determination for patients under ITI treatment

- Medical History
- Concomitant Medication will be recorded throughout the trial
- Physical examinations will be performed at screening, at six monthly visits and at the completion visit.

5 **STUDY POPULATIONS**

5.1 **Subject Disposition**

For the analysis of this study the following populations will be considered:

- **Safety analysis population**: All subjects who received at least one dose of *Human-cl rhFVIII*
- **Intent to Treat (ITT) analysis population**: All subjects in the safety analysis population for whom any data was collected post treatment with *Human-cl rhFVIII*

Subpopulations of the ITT population will be

- Subjects of each ethnic group
 - Subjects with ITI treatment
 - Subjects with breakthrough bleedings, if appropriate
 - Subjects with surgical interventions, if appropriate
 - Subpopulations especially for inhibitor incidence analysis:
 - Subjects with different F8 gene mutations
 - Subjects with/without family history of inhibitors
 - Subjects by classes of EDs prior to inhibitor generation (1-5, 6-10, 11-20, 21-50, > 50)
 - Subject's age at first exposure (< 1, 1-6, > 6-12, > 12 months)
 - Subjects by reason for treatment prior to inhibitor generation
 - Subjects by intensity of treatment with/without peak treatment moments before inhibitor appearance (peak treatment moments defined as
 - ≥ 3 subsequent days with FVIII dosing, and/or
 - at least one day with prophylactic doses of > 50 IU FVIII /kg BW)
 - ED50 sub-population: Patients in the ITT population with at least 50 EDs of treatment with *Human-cl rhFVIII*
 - ED20 sub-population: Patients in the ITT population with at least 20 EDs of treatment with *Human-cl rhFVIII*.
- **Efficacy: Per Protocol (PP) analysis population**: All subjects in the ITT analysis population who completed the trial without significantly violating the inclusion/exclusion criteria or other aspects of the protocol considered to potentially affect the efficacy results.
Especially the following subjects will be excluded from this population:
 - Subjects who violate the following inclusion criteria:
 - severe haemophilia A (FVIII:C < 1%; historical value as documented in subject records),
 - no previous treatment with FVIII concentrate or other blood products containing FVIII
 - Subjects who fulfil at least one of the following exclusion criteria:
 - other coagulation disorder than haemophilia A
 - severe liver or kidney disease (ALT and AST levels >5 times of upper limit of normal, creatinine >120 $\mu\text{mol/L}$),
 - concomitant treatment with any systemic immunosuppressive drug,
 - Subjects who use concomitant medication that may confound study results, like e.g. alpha-interferon or prednisone
 - Subjects with significant non-compliances with the protocol like for example non-compliance to complete the diary in a proper manner or more than 30% of haemostatic efficacy assessments missing.

- Subjects with dosing or treatment errors like e.g. the use of other FVIII products (except for emergencies) or several *unexplained* and significant deviations from the recommended dose regimen.
- Subjects for whom less than a minimum of inhibitor tests is available*
- Patients with less than 95 days of exposure to *Human-cl rhFVIII*.

*Defined during Data Review Meeting for the interim analysis on April 7, 2016:

if less than 1 inhibitor test is available for any of the following periods:

- baseline, if first result of inhibitor screening after first exposure to the study drug is positive (it cannot be assured that the patient is a PUP),
- between ED2 and ED20,
- between ED21 and ED50.

- Population of subjects on prophylactic treatment schedule (PROPH): All subjects in the ITT population who have at least one prophylactic treatment. Only data under prophylaxis will be used for the analyses.
- Per-protocol population of subjects on prophylactic treatment schedules (PROPH-PP): All subjects in the PP population who have at least 95 EDs of treatment and who have no significant dosing or treatment errors, like e.g. unexplained interruptions of the prophylaxis with *Human-cl rhFVIII*.
- Population of subjects on continuous prophylaxis (PROPHcont): All subjects in the ITT population who have at least one prophylactic treatment and have been assigned to the subgroup of patients receiving continuous prophylaxis, i.e. prophylactic treatment period of at least 169 calendar days, and have not received a mixture of on-demand and prophylactic treatment (however, subjects who were treated on-demand only once and switched to prophylactic treatment thereafter, will be kept in this population).
- Population of subjects with on-demand treatment (OD): All subjects in the ITT population with at least one period of on-demand treatment. Only data under on-demand treatment will be used for the analyses.
(Definition of period under OD: A patient in the main study is defined to be under prophylaxis during all time periods within 14 days after each prophylactic treatment. A patient in the main study is defined to be under OD in time periods he is not under “Prophylaxis” according to previous definition)
- Population of BEs (BLEED): All documented treated BEs of subjects in the ITT population for which
 - any amount of treatment with *Human-cl rhFVIII* is documented (either the treatment is indicated with reason “Bleeding” or ITI treatment and an efficacy assessment for the BE is documented).
 - start between first BE treated with *Human-cl rhFVIII* and the completion visit*Note*: Any type of BE is included: spontaneous, traumatic, post-operative or other

Additional to version 2.0 of the SAP, part of the analysis will be restricted to BEs during inhibitor-free periods.

- Population of BEs per protocol (BLEED-PP): All documented bleeds in the BLEED population of subjects in the PP population, which
 - are *not* treated with another FVIII or bypassing agents

Note: Any type of BE is included: spontaneous, traumatic, post-operative or other

Additional to version 2.0 of the SAP, part of the analysis will be restricted to BEs during inhibitor-free periods.

- Surgery population (SURG): All documented surgical interventions of subjects in the ITT population for which
 - any amount of *Human-cl rhFVIII* prior to, during or after the surgery is documented and
 - no other FVIII concentrate is documented within 24 hours prior to surgery*.
- Surgery per-protocol population (SURG-PP): All documented surgical interventions of subjects in the PP population for which
 - any amount of *Human-cl rhFVIII* prior to, during or after the surgery is documented and
 - no other FVIII concentrate is documented within 72 hours prior to, during or after the surgery (until resuming regular prophylactic treatment or until discharge from hospital in case of a subject with on-demand treatment).

*For the analyses of surgeries only surgeries performed under *Human-cl rhFVIII* will be considered; clearly the assessment of the efficacy of *Human-cl rhFVIII* in surgeries should not be biased by inclusion of data from surgeries where other FVIII concentrates were used prior to the surgery.

Additional to version 2.0 of the SAP, part of the analysis will be restricted to surgeries during inhibitor-free periods.

- Infusions analysis population (Safety-INF): All documented infusions with *Human-cl rhFVIII* to subjects of the Safety population.
For the definition of temporally associated AEs: AEs will be related to a subject's infusion No. i, if the AE starts during infusion No. i or within 24 hours after infusion No. i, but before the same subject's infusion No. i+1.

The subject disposition, i.e. the identification of significant deviations to consider for the PP population and the assignment of each subject, bleeding and surgery to these analysis populations, will be the joined decision of the trial statistician and the responsible medical expert prior to database lock.

There may be further reasons to exclude patients from analysis populations without an underlying protocol deviation. This comprises:

- Patients withdrawn from study according to protocol with incomplete data.

The ITT analysis is considered to be most relevant for the analysis of immunogenicity data; the PROPH population is considered to be most relevant for the analysis of efficacy data on prophylaxis; the BLEED population is considered to be most relevant for the analysis of efficacy data on treatment of bleeds and the SURG population is considered to be the most relevant for the analysis of efficacy data on treatment during surgeries. To evaluate the robustness of the study results, efficacy analyses will also be done based on the PP population.

5.2 **Protocol Deviation Assessment**

Protocol deviations will be assessed as major or minor with respect to the analysis populations defined in section 5, and listed as part of the database release procedures prior to data analysis, and will include:

- Violation of inclusion or exclusion criteria
- Concomitant medication that may confound study results (see protocol chapter 4.2.2 Forbidden Concomitant Medication)
- Non-compliance issues raised by the investigator or sponsor.
Dosing or treatment errors like e.g. the use of other FVIII products (except for emergencies) or significant deviations from the recommended dose regimen.
- Less than a minimum of inhibitor tests (see Chapter 5.1, definition of PP population) available
- Less than 100 days of exposure to *Human-cl rhFVIII* at completion (< 95 EDs is regarded as major, 95-99 EDs is regarded as minor protocol deviation; if an inhibitor is detected prior to 95 EDs and the patient switched to ITI treatment, this is not regarded as a protocol deviation)

A list of major protocol violations will also be included in the Clinical Study Report.

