## 4.1.1 Inclusion Criteria

In order to qualify for study enrolment, the following criteria must be fulfilled before study entry:

- 1. Male patients
- 2. Severe Haemophilia A (FVIII:C < 1%)
- 3. No previous treatment with FVIII concentrates or other blood products containing FVIII
- 4. Voluntarily given, fully informed written and signed consent given before any studyrelated procedures are conducted (obtained from the patient's parent(s)/legal guardian(s))

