# 9.2.1 Population for Analysis

For the analysis of this study, the following populations will be considered:

- Safety analysis population: All subjects who received at least one dose of *Human-cl rhFVIII*;
- Intent to Treat (ITT) analysis population: All subjects in the safety analysis population for whom any data was collected post treatment with *Human-cl rhFVIII*;
- Efficacy: Per Protocol (PP) analysis population: All subjects in the ITT analysis population who completed the trial without significantly violating the inclusion/exclusion criteria or other aspects of the protocol considered to potentially affect the efficacy results. Especially the following subjects will be excluded from this population:
  - Subjects who violate the following inclusion criteria:
    - severe Haemophilia A (FVIII:C <1%; historical value as documented in subject records),
    - No previous treatment with FVIII concentrates or other blood products containing FVIII
  - Subjects who fulfil the following exclusion criteria:
    - other coagulation disorder than Haemophilia A
    - severe liver or kidney disease (ALT and AST levels >5 times of ULN, creatinine >120 μmol/L),
    - concomitant treatment with any systemic immunosuppressive drug
    - subjects who use concomitant medication that may confound study results, like e.g. alpha-interferon or prednisone
  - Subjects with significant non-compliances with the protocol such as non-compliance to complete the diary in a proper manner or more than 30% of haemostatic efficacy assessments missing.
  - A minimum of inhibitor tests (baseline, after 1-4 EDs, 10-15 EDs and 50 EDs) is available
  - Subjects with dosing or treatment errors like e.g. the use of other FVIII products (except for emergencies as mentioned above) or several *unexplained* and significant deviations from the recommended dose regimen.
  - Patients with less than 100 days of exposure to *Human-cl rhFVIII*.

- Subpopulations of the ITT populations will be
  - Subjects of each ethnic group
  - Subjects with ITI treatment
  - Subjects with breakthrough bleedings, if appropriate
  - Subjects with surgical interventions, if appropriate
  - Subpopulations especially for inhibitor incidence analysis:
    - Subjects with different FVIII gene mutations
    - Subjects with/without family history of inhibitors
    - Subjects by classes of EDs prior to inhibitor generation
    - Subjects by reason for treatment prior to inhibitor generation

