3.4 Assessment of Objectives

3.4.1 Immunogenicity

The *primary objective* is to investigate the immunogenicity of Human-cl rhFVIII.

The *primary endpoint* is the incidence of inhibitors within the observation period. For one patient an inhibitor is assessed to be positive if the modified Bethesda assay (Nijmegen modification) results in a titer ≥ 0.6 BU at any time point during the observation period.

Inhibitor activity will be determined centrally at the following time points: At baseline (Screening Visit), every 3-4 EDs until ED 20, every 10-12 EDs or every 3 months \pm 2 weeks after ED 20 (whichever comes first), at study completion; at any time in the case of a suspicion of inhibitor development.

In case of a positive inhibitor result, an inhibitor re-testing using a second separately drawn sample should be performed centrally; the result of the second sample will be taken as the final result for the time point. Low titre inhibitors will be defined as ≥ 0.6 to < 5 BU, high-titre inhibitors will be defined as ≥ 5 BU.

Patients who develop a non-transient inhibitor will have an option to start ITI treatment. Patients developing inhibitors and not starting ITI within one year after inhibitor detection will be

withdrawn from the study. Inhibitors that 'disappear' without any clinical signs or symptoms, where no FVIII dosing increase was required, and that turn back to <0.6 BU within a period of 6 months after first detection are regarded as "transient". Patients who develop such a transient inhibitor will continue regular treatment within the study until they have reached ED 100 or a maximum period of 5 years.

Definition of inhibitor confirmation and time to inhibitor occurrence:

Occurrence of inhibitors:

For these definitions inhibitor titres determined in the central laboratory are considered.

(I1) FVIII:C high titre inhibitor occurrence is confirmed, if

inhibitor level ≥ 5 BU at one time point $t_{1,H}$ and

- inhibitor level confirmed to be ≥ 5 BU at a subsequent* time

point $t_{2,H}$ or

- retest of sample from *any* time point $t_{3,H}$ ($=t_{1,H}, t_{2,H}$ or later) confirmed to be ≥ 5 BU.

* 'Subsequent' in the context of this document always means 'at a later time point' or 'in a later sample', but not necessarily the immediate consecutive visit or sample.

(I2) FVIII:C Inhibitor occurrence in a patient is confirmed, if

- a high titre inhibitor is confirmed according to (I1)

or if

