- inhibitor level ≥ 0.6 BU at one time point $t_{1,I}$

and retest of sample from same time point $t_{1,I} \geq 0.6$ BU

and inhibitor level ≥ 0.6 BU at a subsequent time point

or

- inhibitor level ≥ 0.6 BU at one time point $t_{1,I}$

and inhibitor level ≥ 0.6 BU at a subsequent time point

and retest of sample from same time point $t_{2,I} \geq 0.6$ BU

or

- inhibitor level ≥ 0.6 BU at three subsequent time points $t_{1,I}, t_{2,I}$ and $t_{3,I}$
(e.g. if retests are not available).

(I3) An inhibitor is confirmed to be a low titre inhibitor, if

- occurrence of inhibitor of < 5 BU is confirmed (according to I2) but

- occurrence of high titre inhibitor (according to I1) is *never* confirmed during the observation period*

(Note: a low titre inhibitor which turns to a confirmed high titre inhibitor according to definition I1 is solely counted as a high titre inhibitor. Inhibitors initially measured as low titre of < 5 BU and remain low titre (< 5 BU) are defined as low titre inhibitors)

*This condition means that a patient only can be defined as having either a low titre inhibitor or a high titre inhibitor. The patient cannot be counted twice.

These definitions for confirmation of positive inhibitors and for high and low titre inhibitors are considered to be relevant for the overwhelming number of inhibitor occurrences. However, there might be cases where additional information (e.g. when taking the whole sequence of inhibitor testing or additional local lab data into account) may suggest that an inhibitor may be assessed rather high titre than low titre. All inhibitor data will be reviewed during the Data Review Meetings before interim analysis/ final analysis to identify such cases.

Time and number of EDs until inhibitor occurrence:

(I4) The time / number of EDs to inhibitor occurrence is defined

- by the time between ED1 and the date of the first positive inhibitor titre detected in a confirmed

inhibitor patient (I2)

- more exactly : as

minimum {date of $t_{1,H}$, date of $t_{1,I}$ } – date of Day 1 (ED1) (days) ,

or the number of EDs (with injections for any indication) during this time frame (ED1 until day before minimum {date of $t_{1,H}$, date of $t_{1,I}$ })

(Note: If different dates for $t_{1,H}$ and $t_{1,I}$ are available, the earlier date will be taken into account)

Censoring: Time / number of EDs until any inhibitor will be censored for patients without inhibitor at date of last available inhibitor testing

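### The SAP's per-protocol rule excludes a patient with no baseline inhibitor test only if his first post-exposure test is positive, so per-protocol inhibitor incidence is selected on the outcome and biased slightly downward

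*SAP*

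**What the plan says.** Protocol 9.2.1 sets the inhibitor tests needed for PP: "A minimum of inhibitor tests (baseline, after 1-4 EDs, 10-15 EDs and 50 EDs) is available". The baseline item carries no condition.

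SAP 5.1 replaces this with a footnote to the PP definition, introduced as "Defined during Data Review Meeting for the interim analysis on April 7, 2016". A patient fails the minimum "if less than 1 inhibitor test is available for any of the following periods": baseline, ED2 to ED20, and ED21 to ED50. The two later periods carry no condition on results. The baseline period does: "baseline, if first result of inhibitor screening after first exposure to the study drug is positive". The reason given is that "it cannot be assured that the patient is a PUP".

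SAP 5.1, like protocol 9.2.1, names ITT as the most relevant population for immunogenicity. SAP section 13 nevertheless plans the inhibitor incidence tables (14.2.1.1, 14.2.1.2) and the Kaplan-Meier, life-table, logistic and Cox outputs (14.2.3 to 14.2.6) for both ITT and PP.

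On a positive baseline titre the documents are silent. The nearest entry criterion (protocol 4.1.1) concerns treatment history: "No previous treatment with FVIII concentrates or other blood products containing FVIII". The endpoint in SAP 3.4.1 counts a titre of 0.6 BU or more "at any time point during the observation period". Definition I4 sets the time to occurrence "by the time between ED1 and the date of the first positive inhibitor titre detected in a confirmed" inhibitor patient.

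**The concern.** Take two patients who both lack a baseline test. Under the SAP, one stays in PP and the other leaves, and the only difference is a post-exposure inhibitor result. That result is the event that the PP inhibitor tables count. Among patients without a baseline test, the rule removes events and keeps non-events, so PP incidence can only move down.

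The stated reason does not fully carry the rule. Doubt about previously untreated status is plausible when the first test soon after first exposure is positive, but the rule sets no limit on when that first result falls. The only other early requirement is one test between ED2 and ED20, so a first result as late as ED20 would trigger exclusion. Protocol 1.1 says that inhibitors usually arise within the first 50 EDs, so a positive at that point may well be a new inhibitor.

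At stake is the use of PP as a supportive check on the ITT incidence. A check whose membership depends on the outcome is weakened for that purpose.

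**Working it through.** **Inputs.** The documents give no figure for this effect, so there is none to reproduce.
- Patients: 100, the planned number (SAP 4.2), all assumed otherwise eligible for PP.
- Inhibitor incidence: 30%, the upper figure in protocol 1.1, used as an illustration.
- M, the number of patients with no baseline test: not in the documents; assumed 5 to 10.
- f, the share of inhibitor patients already positive at their first post-exposure test: not in the documents; assumed 20% to 60%.
- Missingness is taken as unrelated to outcome, and only patients who have an inhibitor are taken to be positive at the first test.

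**Formula.** Of the M patients, 0.3M have an inhibitor and 0.3Mf are positive at the first test. The SAP rule removes those 0.3Mf from both numerator and denominator:

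PP incidence = (30 − 0.3Mf) / (100 − 0.3Mf)

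| M | f | Calculation | PP incidence | Shift (points) |
|---|---|---|---|---|
| 5 | 0.2 | 29.7/99.7 | 29.8% | −0.2 |
| 5 | 0.6 | 29.1/99.1 | 29.4% | −0.6 |
| 10 | 0.2 | 29.4/99.4 | 29.6% | −0.4 |
| 10 | 0.6 | 28.2/98.2 | 28.7% | −1.3 |

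Outside that range, M = 20 and f = 1 gives 24/94 = 25.5%, a shift of −4.5 points. In general form, with incidence p and missing share m, PP incidence is p(1 − mf)/(1 − mpf). For p from 15% (assumed) to 44.5% (the recombinant-FVIII figure in SAP section 2), m from 5% to 20% and f from 10% to 100%, the shift runs from −0.06 to −5.4 points and is always downward.

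**Within the patients lacking a baseline test**, apparent incidence is 0.3(1 − f)/(1 − 0.3f). For f = 0.2 this is 0.24/0.94 = 25.5%; for f = 0.6 it is 0.12/0.82 = 14.6%. No planned table reports this subgroup; the figures show the mechanism only.

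**Whole-patient example.** There are 100 patients and 30 inhibitors; 10 patients lack a baseline test, and 3 of those have inhibitors. Exact 95% intervals:
- SAP rule, 1 of the 3 positive at first test: 29/99 = 29.3% (20.6 to 39.3).
- SAP rule, all 3 positive at first test: 27/97 = 27.8% (19.2 to 37.9).
- Baseline required of everyone: 27/90 = 30.0% (20.8 to 40.6).

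**Positive pre-dose titre (a separate matter).** The minimum-tests rule checks whether a result exists, not what it is. Suppose a pre-dose positive is followed by a later positive that is confirmed on retest. I2 is then met, and I4 takes the pre-dose date as the start, so the time from ED1 is zero or less. One such patient counted as an event, against leaving him out: 31/100 − 30/99 = 31.0% − 30.3% = +0.7 points. This applies to ITT as well as PP.

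**The case against.** The strongest reply is that the rule is a reasoned attribution rule in a supportive population. A negative first post-exposure test is itself evidence against a pre-existing inhibitor, so a missing baseline matters less there. After a positive first test, an old and a new inhibitor cannot be told apart. ITT leads for immunogenicity, the trial is descriptive, and the SAP's robustness sentence speaks of efficacy analyses. Baseline screening is scheduled for every patient, and nothing shows that any test is missing. Tests are due every 3-4 EDs until ED 20, so a first result at ED20 would mean several missed tests, which might count as significant non-compliance. The shift is small against a 95% interval nearly 20 points wide.

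Most of this stands and limits the size of the problem. It does not remove it. A missing baseline followed by a negative test leaves the same gap in the record, yet that patient stays. The SAP places immunogenicity under its evaluation of efficacy and plans the full set of PP inhibitor outputs. The non-compliance rule gives no threshold for missed inhibitor tests.

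A reader might also infer that keeping a baseline-positive patient is part of the same selection. It is not: that is possible misclassification of an existing inhibitor as incident, and it pushes incidence up. Nor does a lone positive baseline count as an event, because I1 and I2 require further positive results. He stays in PP only by omission: the exclusion list is explicitly not exhaustive, documented prior FVIII treatment would exclude him, and PP assignment is decided jointly before database lock.

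**Conclusion.** The concern holds for the PP inhibitor analyses. The SAP makes PP membership depend on a post-exposure inhibitor result where the protocol does not, and the resulting bias is downward. At 30% incidence it is about 0.2 to 1.3 points for 5 to 10 missing baselines per 100 patients and 20% to 60% first-test positivity. Both ranges are assumptions. If no baseline tests are missing, there is no effect. If some patients dropped for a first positive never have a confirmed inhibitor, the bias is somewhat smaller.

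Two stronger readings are not supported. The first is that the primary result is biased by this rule: ITT membership does not depend on it. The second is that the rule was shaped to lower the inhibitor rate because it was set at a data review meeting during the trial: the documents foresee such meetings and give a genuine reason for the rule, and the date alone shows no intent.

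The silence on positive pre-dose titres is a secondary gap. It matters only if such a patient exists and is later confirmed under I1 or I2. It would then add about 0.7 points per patient and give an invalid event time.

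**What to change.** **SAP 5.1.** Replace the conditional baseline item with one that uses pre-dose information only: PP requires an inhibitor sample drawn before the first Human-cl rhFVIII dose, whatever the later results. List the patients excluded for a missing baseline, with their later inhibitor status.

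**SAP 3.4.1, definitions I2 and I4.** Count only positives from samples drawn after first exposure. Report any confirmed pre-dose positive separately, and give ITT incidence with and without him.

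**Cost.** SAP wording and one listing; baseline inhibitor results are already in Listing 16.2.8.2. The price is that inhibitor-negative patients without a baseline test also leave PP. In the whole-patient example that is 7 of the 10, with PP falling from 97 to 90 and the interval widening from 18.7 to 19.8 points. If the SAP can no longer be changed, the same analysis can be added as a supplementary PP table.
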